30.0 Community-Based Participatory Research

- This is not a community-based participatory research project – [please leave the rest of this section blank](#)
- This is a community-based participatory research project
[Describe the involvement of the community in the design and conduct of the research.](#)

[Click here to enter text.](#)

Note: Community based research is research that is conducted as an equal partnership between academic investigators and members of a community. In Community Based Participatory Research (CBPR) projects, the community participates fully in all aspects of the research process.

31.0 MULTI-SITE RESEARCH (when CWRU is the IRB of Record)

Does this project have multiple sites?

- Yes
- No – [please leave the rest of this section blank](#)

Non-Local Site Information for Multi-Site Studies

If this is a multi-site study where you are the lead investigator, list the following information for each relying site:

1. Name of site: [Click here to enter text.](#)
2. PI of relying site: [Click here to enter text.](#)
3. Name of IRB contact: [Click here to enter text.](#)
4. Phone number of IRB contact: [Click here to enter text.](#)
5. Email address of IRB contact: [Click here to enter text.](#)

Non-Local Recruitment Methods for Multi-Site Studies

If this is a multi-site study and research participants will be recruited by methods not under the control of the local site (e.g. call centers, national advertisements) describe those methods.

Local recruitment methods are described above.

1. *Describe when, where, and how potential research participants will be recruited.* [Click here to enter text.](#)
2. *Describe the methods that will be used to identify potential research participants.* [Click here to enter text.](#)
3. *Describe the materials that will be used to recruit research participants.* [Click here to enter text.](#)

Multi-Site Research Communication Plan (when you are the lead investigator)

If this is a multi-site study where you are the lead investigator, describe the processes to ensure communication among sites including:

- All sites will have the most current version of the protocol, consent document, and HIPAA authorization
- All required approvals (initial, continuing review and modifications) have been obtained at each site (including approval by the site's IRB of record)
- All modifications have been communicated to sites, and approved (including approval of the site's IRB of record) before the modification is implemented
- All engaged participating sites will safeguard data, including secure transmission of data, as required by local information security policies
- All engaged participating sites will safeguard data, including secure transmission of data, as required by local information security policies
- All local site investigators conduct the study in accordance with applicable federal regulations and local laws
- All non-compliance with the study protocol or applicable requirements will be reported in accordance with local policy

If this is a multi-site study where you are the lead investigator, describe the method for communicating to engaged participant sites the following:

1. *Problems*: Click here to enter text.
2. *Interim results*: Click here to enter text.
3. *The closure of the study*: Click here to enter text.

**CASE WESTERN RESERVE
UNIVERSITY
Frances Payne Bolton
School of Nursing**

[name], RN, FAAN
Associate Professor
Agnes Stahlin Baun Scholar

Nursing Research Building
[name]
[name]
Health Education Campus
[name]
[name]
[name]

[contact]
[contact]
[contact]

Date: May 14, 2021

Title of Study: Self-Management in Young Adults with Type 1 Diabetes

ClinicalTrials.gov ID: NCT04975230

Please find the statistical analysis plan for this study.

Sincerely,

A handwritten signature in black ink that reads "[name]".
[name], RN

Statistical analyses. Descriptive statistics will summarize each of the variables over the monitoring period, post-intervention (3-months), and 6-months for the intervention and control groups. The general estimating equation (GEE) will be used to estimate the difference in changes from baseline to post-intervention (3 months), and at a 6-month follow-up for primary and secondary outcomes, including each baseline outcome as a covariate. The hypothesis will guide the analyses that the intervention will improve total sleep time, interdaily stability, intradaily variability, and glycemia. However, our objective is not statistical significance but the determination of preliminary effect sizes. GEE will be used to estimate the statistical power necessary to conduct a larger clinical trial.

Sample size justification. We plan to enroll 48 participants to attain a final sample of 40 participants (20 per group) accounting for an estimated attrition of 20%. This sample size is based on previous studies on sleep and glycemia in young adults and adolescents with T1D⁶⁹ and pilot sleep intervention studies in young adults.⁶⁸ **A power calculation for sample size was not conducted due to the pilot nature of the study and our sample is in line with several research papers on an appropriate pilot sample size. A sample of 40** participants (20 per group) will allow us to determine a Cohen's eta effect size with 95% CI for group differences at post-intervention (3 months) with bias-corrected limits of [.00 -.14], [.00 -.24], and [.01 -.34] for small ($n^2 = .01$), medium ($n^2 = .06$), and large ($n^2 = .14$) effect sizes respectively.

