2.0 Objectives

Directions: Describe the purpose, specific aims or objectives. Be sure to also include the hypothesis being tested. The purpose of this study is to characterize sleep health (quantity, quality, timing, variability), diabetes-self-management, symptoms (general diabetes and emotional), and glycemia (glycemic control and glucose variability) over 7 days in young adults age 18-25 years with type 1 diabetes (T1D) during the COVID-19 pandemic. Aim 1. Determine the prevalence of clinically significant emotional distress, diabetes distress, high-risk sleep apnea, and clinically significant insomnia in 200 young adults with T1D and compare to the prevalence of the general T1D population pre-pandemic. Aim 2. Examine the associations between sleep health, diabetes self-management, symptoms, and glycemia in 200 young adults with T1D. Aim 3. Determine the additional contribution of sleep (quantity, quality, timing, or variability) to the variance in symptoms, diabetes self-management, and glycemia in 200 young adults with T1D. Aim 4. Elicit feedback on a behavioral sleep self-management intervention from 10 young adults with T1D who are at low risk for sleep apnea and do not meet the threshold for clinically significant insomnia.

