5.0 Number of Research Participants

Directions: Indicate the target number of research participants to be accrued locally, and, if this is a multi-site study, indicate the total number of research participants to be accrued across all sites.

Example language that can be used: *We will enroll 25 subjects at CWRU and plan to enroll 150 subjects study wide.* We will enroll 200-300 participants for aims 1-3 and will invite 10-15 participants from aims 1-3 to complete aim 4

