1) This is a multi-method descriptive study using both quantitative and qualitative methods to describe the phenomenon of interest. For Aims 1-3 an online survey will be administered at baseline with twice daily surveys over a one-week period. All surveys will be administered in REDCap. The final questions in the online survey will be if participants are willing to participate in a focused interview via zoom to see the components of a sleep self-management intervention. The presentation and interview (zoom) will be audio recorded and transcribed verbatim. The interview will be conducted with each participant individually. Only those at low risk for sleep apnea and who do not meet the threshold for clinically significant insomnia will be invited to participate in aim 4. For aim 4 we will engage 10-15 emerging adults with T1D on zoom to provide input on content, format, delivery, as well as barriers/facilitators of the proposed intervention. We will partner with the participants and will use a community-engaged approach to increase the likelihood that the intervention will be relevant and acceptable to them. We are presenting a potential intervention and will not be delivering an actual intervention to get feedback on the initial one-hour session. We will collect quantitative and qualitative data and then use the findings to develop the intervention protocol. We will ask participants to provide input on how to deliver the weekly follow ups for the next phase (e.g., text, phone call, zoom, or email) and every 3-week booster sessions (e.g., in person vs. zoom). 2). All quantitative data will be de-identified and exported from REDCap and analyzed in SAS or SPSS. Both the presentation and interviews will be audio-recorded and transcribed verbatim. The recordings and transcripts will be housed on a case research server and not stored directly on a hard drive. The transcripts will be de-

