14.0 ClinicalTrials.gov Information

Directions: If this study has been registered on ClinicalTrials.gov, provide the ClinicalTrials.gov identifier and the investigator/sponsor responsible for registering. If this study has not been registered on ClinicalTrials.gov, provide the rationale as to why and if/when it will be. If it does not meet the requirement for being registered on ClinicalTrials.gov, please state that.

N/A this is not a clinical trial

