27.0 Provisions to Monitor the Data to Ensure the Safety of Research Participants

1. Describe how often the data will be monitored for completeness, accuracy and adherence to the protocol. N/A this is a cross sectional design. Data will be collected once for aims 1-3 and once for aim 4 as this is not a repeated measures design.
2. Indicate if there will be a Data and Safety Monitoring Board or Committee:
 - There will not be a formal Data and Safety Monitoring Board/Committee.
 - There will be a formal Data and Safety Monitoring Board/Committee.

Provide information about the DSMB/C including the contact information of the committee member(s) (as applicable); whether it is independent from the study sponsor; how often it meets; the type of data that will be used; written reports, etc. Click here to enter text.

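### The SAP plans a two-arm pilot with 3- and 6-month follow-up, but the protocol is a one-group, one-week survey; the SAP has no analysis for Aims 1-3, and protocol section 16 covers Aim 3 only in part

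*SAP*

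**What the plan says.** **SAP.** The statistical analyses paragraph opens: "Descriptive statistics will summarize each of the variables over the monitoring period, post-intervention (3-months), and 6-months for the intervention and control groups". It then names GEE for the difference in change from baseline to 3 months and to 6 months, adjusted for the baseline value. The hypothesis is that the intervention improves total sleep time, interdaily stability, intradaily variability and glycemia. On size it says: "We plan to enroll 48 participants to attain a final sample of 40 participants (20 per group", with 20% attrition allowed for and no power calculation. The covering letter presents the text as the plan for this study.

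**Protocol.** Section 5.0: "We will enroll 200-300 participants for aims 1-3". Section 12.0: "For Aims 1-3 an online survey will be administered at baseline with twice daily surveys over a one-week period". On the sleep programme shown to Aim 4 interviewees, section 12.0 says: "We are presenting a potential intervention and will not be delivering an actual intervention". Section 14.0, on registration, answers: "N/A this is not a clinical trial".

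Aim 3 in section 2.0 reads: "Determine the additional contribution of sleep (quantity, quality, timing, or variability) to the variance in symptoms, diabetes self-management, and glycemia". Section 16.0 is the protocol's own analysis plan. For Aim 1 it gives descriptive statistics. For Aims 2-3 it gives correlations, a linear regression of variables that correlate at .3 or more, a regression of glycemic control on self-management, and a set of mediation equations.

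**The concern.** A SAP is meant to fix how the protocol's data will be analysed. Here it specifies a contrast between two groups at two later visits, and the protocol creates neither the groups nor the visits. Anyone following the SAP would have nothing to fit for Aims 1-3 and would have to fall back on section 16.

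Section 16 is a real plan, but for Aim 3 it is incomplete. Where it states no test, the model, the sleep variables and the order of entry could be chosen after the data are seen. The SAP's sample-size argument, which concerns precision with 20 per group, also says nothing about the survey's 200-300.

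**Working it through.** **1. The SAP's own figures.** Inputs: 40 final, two groups, 20% attrition (SAP, sample size justification).

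- Enrolment: 40 × 1.2 = 48, the stated figure. Dividing by the retained fraction gives 40 / 0.8 = 50, and 48 × 0.8 = 38.4. The difference is small and is not the point here.
- Precision: with one between-group degree of freedom and 40 − 2 = 38 residual, F = η² / (1 − η²) × 38, which is 0.384, 2.426 and 6.186 for η² = .01, .06 and .14. Inverting the noncentral F gives 95% limits of [.000, .142], [.000, .238] and [.004, .337]. The SAP states [.00, .14], [.00, .24] and [.01, .34]. Only the last lower limit differs.

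The SAP's numbers are therefore coherent for a 40-person, two-group comparison.

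**2. What the SAP needs, set against what the protocol provides.**

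| Element | SAP | Protocol |
|---|---|---|
| Delivered intervention | yes | none (section 12.0) |
| Control group | yes | none defined |
| 3-month assessment | yes | none; one week of surveys (section 12.0) |
| 6-month assessment | yes | none |
| Enrolment | 48 | 200-300 (section 5.0) |

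The protocol has 0 of the 4 design elements. Its enrolment is 200 / 48 = 4.2 to 300 / 48 = 6.3 times the SAP's. The timeline table in section 13.0 is unfilled template text and supplies no visit. Interdaily stability and intradaily variability, named in the SAP's hypothesis, do not appear in the protocol.

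**3. Aims 1-3 in the SAP.** The SAP contains no prevalence estimate, reference comparison, correlation, cross-sectional regression or mediation analysis. Its descriptive statistics are by arm and visit. Quantitative aims covered: 0 of 3.

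**4. Aim 3 in section 16.** Aim 3 names three outcome domains (symptoms, self-management, glycemia) and four sleep dimensions (quantity, quality, timing, variability), which makes 3 × 4 = 12 combinations. The stated analyses cover them as follows.

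- *Mediation, first equation:* sleep is the outcome and self-management the predictor. This does not test what sleep adds to anything.
- *Mediation, third equation:* sleep quantity, quality or timing must affect glycemic control, and self-management is then judged with sleep controlled. With both in one model, the test of a single sleep coefficient is the same as a one-degree-of-freedom R-squared-change test (F = t²). In substance this covers glycemic control with three sleep dimensions: 3 of 12 combinations.
- *Regression of glycemic control on self-management:* no sleep term is stated.
- *Regression of variables with r of .3 or more:* it could include sleep with symptoms or self-management, but no outcome, order of entry or added-variance test is given. A sleep variable correlating below .3 (.3² = 9% of variance) would not enter at all.

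The other 9 combinations have no stated test: symptoms and self-management as outcomes with any sleep dimension (2 × 4 = 8), and sleep variability with glycemia (1). The mediation hypothesis does speak of sleep health variables generally, and section 2.0 counts variability among them, but the equations list only quantity, quality and timing. No R-squared change is stated anywhere.

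**The case against.** The strongest reply is that the survey already has a plan. Section 16 covers Aims 1-3, and its third mediation equation tests sleep against glycemic control with self-management in the model. This stands. A reader might infer from the mismatch that Aim 3 has no test at all, or that the study has no analysis plan; the documents do not support either. Nor is every aim left without a result, since Aim 4 is qualitative and has its own plan in sections 12.0 and 16.0.

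A second reply is that the two files were simply mis-paired. Section 12.0 mentions a next phase with weekly follow-ups and boosters, and the SAP's citations 68 and 69 do not fit items 68 and 69 in the protocol's list, which concern actigraphy. A reader might infer that the SAP belongs to that later pilot. The documents do not confirm this, and the SAP's letter says otherwise. Re-pairing would in any case be a way of making the correction.

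Third, GEE could be fitted to the week of twice-daily surveys. That is true of the method, but not of the SAP's between-group change to 3 and 6 months.

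Fourth, section 27.0 says "Data will be collected once for aims 1-3 and once for aim 4 as this is not a repeated measures design", which looks like decisive support. It sits badly with the twice-daily surveys in section 12.0 and with section 8.0, which calls the study longitudinal over a week. The point does not rely on it.

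Last, a reader might infer that the survey is too small for Aim 3. The figures do not show that. Reading section 16's effect size of 0.13 as f², with two tested predictors as stated there, and assuming alpha 0.05 and 80% power, 78 complete cases suffice. For four sleep variables tested jointly the figure is 97, and power at 0.13 is about 95% with 150 cases and 99% with 200. The defect is one of specification, not of power.

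**Conclusion.** The mismatch is certain on the text. The SAP's between-group analysis and sample size cannot apply to the protocol's data (0 of 4 required elements), and the SAP analyses 0 of 3 quantitative aims. This must be corrected before either document is relied on.

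If the study is the survey, there is a narrower second gap. Section 16 in substance tests sleep quantity, quality or timing against glycemic control. It states no added-variance test for symptoms or self-management, none for sleep variability, and no R-squared change. This rests on reading the third mediation equation as containing both self-management and sleep, which is the reading most favourable to the protocol. Which study was intended cannot be settled from the documents.

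**What to change.** Reconcile the two documents so that both describe one study.

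- **If it is the survey:** replace the SAP's analysis and sample-size text with the section 16 analyses and the 200-300 sample. For Aim 3, add the R-squared change (F test) when the sleep variables are added to a covariate model, separately for symptoms, self-management and glycemia. Enter all the sleep variables, including variability, whether or not they pass the .3 correlation screen. Report the number analysed in each model, because monitor data are shared at the participant's choice, questions may be skipped and partial data are kept. This is a text change with no added procedures. The number available for the glycemia model is not known from the documents.
- **If it is the two-arm pilot:** pair the SAP with a protocol that defines its arms, allocation, 3- and 6-month assessments and outcomes. The cost is small if such a protocol exists. The documents do not show one; if there is none, it must be written and approved.

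### 48 enrolled, 20% attrition and 40 completers cannot all hold: 20% attrition from 48 leaves about 38 (19 per group)

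*SAP*

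**What the plan says.** The SAP's paragraph headed Sample size justification gives enrolment, final sample and attrition in one sentence: "We plan to enroll 48 participants to attain a final sample of 40 participants (20 per group) accounting for an estimated attrition of 20"%. It rests the size on precedent ("This sample size is based on previous studies on sleep and glycemia in young adults and adolescents" with T1D, plus pilot sleep studies and papers on pilot sample size). It says plainly that "A power calculation for sample size was not conducted due to the pilot nature of the study".

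The only computed support is a precision statement. The 40 "participants (20 per group) will allow us to determine a Cohen's eta effect size with 95% CI", and the interval is described as a "95% CI for group differences at post-intervention (3 months) with bias-corrected limits of" .00 to .14, .00 to .24 and .01 to .34, for eta-squared of .01, .06 and .14 respectively.

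The SAP's Statistical analyses paragraph has assessments at 3 and 6 months. The attrition sentence does not say which of the two the 20% refers to. The Protocol (sections 5.0 and 16.0) describes a different design, a survey of 200 to 300 people with an interview component, and has no figure that would reconcile the three numbers.

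**The concern.** Attrition is ordinarily the proportion of enrolled participants who are lost. Read that way, the stated enrolment and attrition do not give the stated final sample. The final sample matters a little beyond the sentence itself, because the same 20 per group is the input to the eta-squared limits. The SAP's stated aim is to obtain preliminary effect sizes, so the expected width of those intervals is the main quantitative claim about what this pilot can deliver.

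There is also a point of practice. The SAP says that this pilot will inform the power of a larger trial. If the same inflation method is carried forward with 20% attrition, enrolment is set at 1.20 times the completers instead of 1/0.80 = 1.25 times. That is 1.20/1.25 = 0.96 of the number needed, a 4% shortfall at any size.

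**Working it through.** **Inputs**, all from the SAP's Sample size justification: enrolled 48; final sample 40 (20 per group, so 1:1 allocation); attrition 20%; limits stated for 20 per group at 3 months.

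**Reproducing the 48.** Adding 20% to the completers gives 40 × (1 + 0.20) = 48, an exact match. This is very probably how the figure arose.

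**Checking the three figures against each other**, with attrition as a share of those enrolled:

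| Held fixed | Formula | Result | SAP states |
|---|---|---|---|
| 48 enrolled, 20% lost | 48 × (1 − 0.20) | 38.4, about 38 (19 per group) | 40 (20 per group) |
| 48 enrolled, 40 final | (48 − 40)/48 | 16.7% | 20% |
| 40 final, 20% lost | 40/(1 − 0.20) | 50 (25 per group) | 48 |

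Ordinary rounding does not close the gap: 38.4 does not round to 40, and 16.7% rounds to 17%.

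**Effect on the eta-squared limits.** The SAP does not describe its bias-corrected method. As an illustration, 95% limits were obtained by inverting the noncentral F distribution with 1 and N − 2 degrees of freedom, F = [η²/(1 − η²)] × (N − 2), and converting each noncentrality limit λ to λ/(λ + N).

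| η² | Upper limit, N = 40 | Upper limit, N = 38 | Change | SAP upper limit |
|---|---|---|---|---|
| .01 | .1415 | .1461 | .0046 | .14 |
| .06 | .2384 | .2434 | .0050 | .24 |
| .14 | .3371 | .3419 | .0048 | .34 |

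At N = 40 the upper limits round to the SAP's own. At N = 38 only the first changes at two decimals (.14 to .15). The match is not complete: the lower limit for η² = .14 is .0035 at N = 40 (.0019 at N = 38), which rounds to .00, whereas the SAP prints .01. The table therefore shows the size of the change only and does not supply replacement limits.

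**Timing.** The number remaining at 3 months depends on when the 20% is lost, which the SAP does not say. Two assumptions give a range:

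- All lost by 3 months: 48 × 0.80 = 38.4, about 38.
- Lost at a constant rate to reach 20% at 6 months: 48 × √0.80 = 42.9, about 43.

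In the second case the 3-month limits for 40 are not too favourable, and only the final number is wrong (38 against 40).

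**The case against.** The strongest reply is that almost nothing turns on this. The gap is 40 − 38.4 = 1.6 expected completers, set against an attrition rate that the SAP itself calls an estimate. No decision rule, error rate or power claim uses 40 rather than 38, and the size is also defended by precedent. That stands, and it is why the point is minor.

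It can also be said that the eta-squared limits are conditional on a sample of 40 and so remain a correct statement about 40 whatever the attrition. That stands too. The criticism is that the plan's own enrolment and attrition do not lead to the sample the limits assume; it does not show that the limits are miscalculated. The size of the change rests on an illustrative method that misses one printed lower limit, so it should be read as an order of magnitude.

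A third reply is that the 20% might be meant relative to completers (8/40 = 20%). The SAP does not say so, and it is not the usual meaning of attrition. A reader who applies 20% to 48 will get 38.

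Finally, the missing time point is a matter of clarity, and the constant-rate scenario rests on no figure in the documents. It is given only to bound the 3-month number.

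**Conclusion.** The inconsistency is real and minor. With attrition taken from those enrolled, 48 and 20% give about 38 completers (19 per group), two fewer than stated. This part needs no assumption beyond the usual meaning of attrition.

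The effect on precision depends on timing. If the full 20% is lost by 3 months, the upper eta-squared limits rise by about .005. If the loss builds up to 6 months at a constant rate, about 43 remain at 3 months and the printed limits are not optimistic. The plausible 3-month range is therefore about 38 to 43. The choice of pilot size is not undermined in either case.

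**What to change.** State one consistent set of figures, and say whether attrition is counted at 3 or 6 months. Any of the following would do:

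- **Keep 48 and 20%.** Give the final sample as about 38 (19 per group). If that loss is expected by 3 months, rerun the three intervals at 19 per group with the SAP's own bias-corrected method; a change of about .005 per upper limit is expected, at most .01 after rounding. Cost: one sentence and three reruns, with no extra participants. This option changes no planning assumption and is the safest default.
- **Keep 48, 40 and the printed limits.** Give attrition as about 16.7% (8 of 48). Cost: one figure. It is suitable only if the investigators actually expect that rate; otherwise it fits the assumption to the answer.
- **Keep 40 and 20%.** Enrol 50 (25 per group). Cost: two more participants, which the size of the discrepancy does not by itself demand.

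Whichever is chosen, the planning of the larger trial should divide by one minus the attrition rate.

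### The SAP labels its eta-squared limits bias-corrected, but they are essentially the ordinary uncorrected limits, and the plan does not settle whether the reported effect size will be corrected

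*SAP*

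**What the plan says.** The SAP plans for a "final sample of 40 participants (20 per group") and states that "A power calculation for sample size was not conducted due to the pilot nature of the study". Precision is offered instead. The sample size paragraph promises that this number "will allow us to determine a Cohen's eta effect size with 95% CI for group differences at post-intervention (3 months"). It then prints three intervals, labelled in this way: "with bias-corrected limits of [.00 -.14], [.00 -.24], and [.01 -.34". They belong, in that order, to eta-squared values of .01, .06 and .14, which the SAP treats as its three benchmark magnitudes. It names no correction, formula or software.

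The analysis paragraph of the SAP plans GEE models "including each baseline outcome as a covariate" and says that "our objective is not statistical significance but the determination of preliminary effect sizes". The estimates are then meant to inform the power of a larger trial. That paragraph names no effect-size estimator. The Protocol does not address the point; the power statement in its section 16.0 concerns a regression analysis.

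**The concern.** Sample eta-squared cannot be negative, so in small samples it overstates the population value. Epsilon-squared, omega-squared and Hedges' g exist to remove most of that bias. A reader who meets the words bias-corrected in a pilot of 40 will assume that this has been dealt with. If the printed limits are the uncorrected ones, the assurance is empty, and nothing else in the SAP says how small-sample bias will be handled when results are reported.

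The pilot's output is an effect size for planning the next trial. An estimate that runs high would make that trial too small.

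**Working it through.** **Inputs.** From the SAP's sample size justification: N = 40, two groups of 20, 95% intervals, η² = .01, .06 and .14. For a two-group contrast df1 = 1 and df2 = 38, or 37 with one baseline covariate.

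**Step 1: reproduce the SAP's limits without any correction.** F = df2 × η²/(1 − η²), which gives:
- 38 × .01/.99 = 0.384
- 38 × .06/.94 = 2.426
- 38 × .14/.86 = 6.186

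Find the noncentrality λ that places F at the 97.5th percentile (lower limit, 0 if there is no solution) and at the 2.5th percentile (upper limit). Each limit is λ/(λ + 40). For η² = .14, λ is 0.142 and 20.34, so the limits are 0.142/40.142 = .0035 and 20.34/60.34 = .3371.

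| η² | SAP | Uncorrected, df2 = 38 | Uncorrected, F = 40 × η²/(1 − η²) |
|---|---|---|---|
| .01 | .00, .14 | .000, .1415 | .000, .1432 |
| .06 | .00, .24 | .000, .2384 | .000, .2427 |
| .14 | .01, .34 | .0035, .3371 | .0052, .3438 |

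The standard formula matches five of six. The variant that uses N = 40 in place of df2 = 38 matches all six.

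**Step 2: the one limit that moves.** The large-effect lower limit is .0035 by the standard formula, .0027 with df2 = 37, .0047 by noncentral t and .0052 by the variant. Only the last rounds to .01. The gap between standard and variant is .0052 − .0035 = .0017.

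**Step 3: look for a correction that gives the stated set.** Negative limits are set to 0.
- Limits moved to the epsilon-squared scale, 1 − (1 − limit) × 39/38: [.00, .12], [.00, .22], [.00, .32].
- Noncentral-F interval built from the corrected point value: about [.00, .20] for medium and [.00, .31] for large.
- The quoted .01, .06 and .14 read as epsilon-squared values that are already corrected: [.00, .20], [.00, .27], [.01, .36].
- Noncentral-t interval built from Hedges' g: [.00, .14], [.00, .24], [.00, .33]. This comes closest, with four of six.
- Bias-corrected bootstrap, simulated averages: about [.00, .11], [.00, .26], [.01, .36].

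None gives the SAP's six limits.

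**Step 4: how far raw η² runs high with 20 per group.** With a true value of 0 its mean is 1/(N − 1) = 1/39 = .026. Simulation gives the rest.

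| True value | Mean raw η² | Mean epsilon-squared |
|---|---|---|
| 0 | .026 | .000 |
| .01 | .035 | .010 |
| .06 | .083 | .059 |
| .14 | .160 | .138 |

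At a true .06 the excess is .083/.06 − 1 = 38%. With no effect at all, 54% of such pilots would show a raw η² of .01 or more. For observed values of .01, .06 and .14, omega-squared = (F − 1)/(F − 1 + 40) is −.016 (reported as 0), .034 and .115.

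**Step 5: what that could do to the next trial.** The SAP gives no design for it, so assume a two-sided 5% t-test with 80% power. With d = 2√(η²/(1 − η²)), a true .06 is d = 0.505 and needs about 63 per group. Planning on .083 (d = 0.602) suggests about 45 per group, at which real power for .06 is about 66%.

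**The case against.** Four objections have weight.

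First, a reader might infer from the mismatch in one lower limit that the SAP's stated precision is wrong. The documents do not support that. Five limits match the standard formula, a simple variant matches all six, and a difference of about .002 before rounding changes neither the widths nor the choice of 20 per group. Noncentral-F limits are limits for the population value, so the upward bias of the sample estimate does not make them wrong. This stands in full.

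Second, a reader might infer that the SAP commits to reporting raw eta-squared. It does not say so. Eta-squared appears only in the sample size paragraph, and the GEE paragraph names no estimator. This stands, and the bias figures are therefore conditional. But eta-squared is the only measure named, and silence does not protect against the bias.

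Third, it goes too far to say that no correction was applied. The SAP names none, so all that can be shown is that none of those checked yields its limits.

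Fourth, it might be feared that the pilot would announce an effect where there is none. The SAP promises a 95% interval and disclaims significance as its aim, and at N = 40 the intervals around small and medium observed effects start at zero. A reader of the results would see that. The concern that remains is the point estimate carried into planning.

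**Conclusion.** The point holds in a narrow form, at minor severity. The bias-corrected label is unsupported, because the limits are essentially those of an uncorrected noncentral-F interval. The widths and the sample-size rationale stand, and the .01 against .00 question is one of convention and rounding.

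The practical issue is the unspecified estimator. If raw eta-squared is what is reported, it will run high by about .02 to .026 on average across the effect sizes considered. That is more than the whole small benchmark of .01.

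The result assumes an unadjusted two-group contrast with 40 completers. Limits from the baseline-adjusted GEE model could differ somewhat. A 20% loss from 48 would leave 48 × .8 = 38.4. With 38 completers the uncorrected intervals are [.00, .15], [.00, .24] and [.00, .34], so the conclusion is the same. The figures of 63, 45 and 66% rest on the assumed t-test design and are illustrative only.

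**What to change.** All changes are to SAP wording:
- Name the method behind the intervals. Delete bias-corrected from the sentence, or name the correction and replace the limits with ones that carry it.
- Give the large-effect lower limit to three decimals, about .004, so that it does not hang on rounding.
- In the analysis paragraph, specify a small-sample bias-corrected effect size with its 95% interval in place of raw eta-squared: omega-squared, epsilon-squared, or Hedges' g for the baseline-adjusted group difference. Name one, and use it when planning the larger trial.

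The cost is that reported effects become slightly smaller: an observed eta-squared of .06 becomes an omega-squared of .034. The sample size and the GEE model do not change.
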